In 2013, Ospemifene was approved by the Food and Drug Administration for the treatment of moderate to severe dyspareunia that is due to menopause [10]. Ospemifene is a non-estrogen selective estrogen receptor modulator (SERM). SERMs are estrogen receptor (ER) agonist/antagonists that typically induce the desirable effects of estrogen while avoiding estrogen-related adverse effects. Unlike other drugs in this class, Ospemifene has been shown to have significant estrogenic agonist effects on the vagina and bone, but antagonist effects on breast tissue [6]. Furthermore, it significantly improves overall sexual function [12]. Despite this promising medical profile, it remains a second or third line of therapy to treat VVA. More research is needed to determine if ospemifene is an acceptable, and possibly a favorable, alternative to vaginal estrogen for the treatment of vulvovaginal atrophy, especially if there is any concern for sexual function. In this research study, we aspire to determine the efficacy of ospemifene compared to a vaginal estrogen. The primary aim of this research is to compare female sexual function as measured by a validated instrument in women randomized to receive ospemifene and vaginal estrogen. Secondary aims include comparing markers of vaginal health and safety in both treatment groups.

Hypothesis

Ospemifene is a nonhormonal alternative that has proven to significantly improve sexual health and vulvovaginal atrophy, yet vaginal estrogen is still considered the first-line therapy. Our null hypothesis is that ospemifene has a similar efficacy as vaginal conjugated estrogens for improving sexual function in postmenopausal women who have vulvovaginal atrophy.

Specific Aims

Specific Aim 1: *To compare the efficacy of ospemifene and vaginal conjugated estrogens on female sexual function.* Ospemifene is the only non-estrogen that is FDA-approved to treat dyspareunia in postmenopausal women. Further, studies report a significant improvement in sexual health in patients that are treated with ospemifene [12]. However, vaginal estrogen therapy (with conjugated equine estrogen or estradiol) remains the most commonly prescribed treatment for dyspareunia. To our knowledge, a direct comparison of ospemifene and local vaginal estrogen therapy on postmenopausal female sexual function has not been performed. We hypothesize that ospemifene provides a greater improvement in sexual function in postmenopausal women with dyspareunia and VVA.

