In essence, Ospemifene seems to be a possible wonder drug for menopausal women. While it's primary use is for VVA-associated dyspareunia, there is consistent evidence of protective activity in bone and breast tissue, while showing no evidence of carcinogenic potential in the endometrium, breast, or liver. Similar to vaginal estrogen, ospemifene has not been studied longer than 12 months to determine long term risks of the medication [6]. Appendix 1 shows a summary of adverse events in various safety studies for vaginal estrogen and ospemifene. Research is

promising that Ospemifene may prove to be a safer and more beneficial choice for all postmenopausal women, regardless of their history of breast or endometrial cancer.

Innovation

Several studies have published data regarding the unique behavior of ospemifene in postmenopausal women. Nonetheless, vaginal estrogen is still seen as the gold standard for the treatment of VVA, regardless of the woman's most bothersome symptom. To our knowledge, for the first time, this study will directly compare the efficacy of vaginal conjugated estrogens and ospemifene in improving sexual function in postmenopausal women who have vulvovaginal atrophy. By also directly comparing symptom improvement with VVA treatment, this study hopes to answer the question of whether or not clinicians should shift towards ospemifene as a first line treatment for sexual dysfunction in postmenopausal women with VVA.

Approach

Overview

This study will be a prospective, randomized study that will compare efficacy and safety of ospemifene and vaginal estrogen. Because of the route of administration for each drug, it is not possible to blind the participants or clinicians to the treatment. However, we will be collecting objective data that cannot be misinterpreted by those collecting and analyzing the data. We hope to effectively inform clinicians who treat postmenopausal women that suffer from VVA about the efficacy of ospemifene as it compares to vaginal conjugated estrogens cream. As a specialty with a high population of patients who complain of VVA, we are very familiar with this patient population, as well as the use of vaginal estrogen in their treatment. This puts this research team in an ideal position to properly execute the study and interpret the findings.

Patient Groups

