Anticipated Results and Interpretation: Similar to objective findings, prior studies have shown significant improvement in VVA symptoms in patients using ospemifene or vaginal estrogen. We anticipate that the improvements seen with ospemifene will be comparable to those seen with vaginal estrogen.

Potential Pitfalls, Alternative Approaches, and Future Directions: The Likert scale is commonly used to assess symptom improvement in VVA treatment studies. We do not anticipate any pitfalls in this specific aim.

Safety Monitoring

Participants in the study will be provided with contact information to be used in the case of an adverse event related to the medication. For emergencies, they will be instructed to dial 911 and/or seek immediate medical attention. They will be instructed to contact the study team at [contact], to inform the team about any adverse event that may be related to the medication.

All reports of injury will be logged in one password-protected electronic file, by members of the study team. Patient data, including adverse events will be reviewed every two weeks by the [name] and [name]. Appendix 1 shows adverse events that have been documented during prior clinical trials of the two medications. This data will be used to determine whether the study will be discontinued due to occurrence or frequency of any given adverse event.

Individual Stopping Rules

Any event that involves new onset of vaginal bleeding, cardiovascular event, venous thromboembolism, or new diagnosis of cancer, will require the individual to discontinue the medication and withdraw from the study.

Timeline

Item	Start	Complete/Submit
IRB application	Started	November 1, 2016
Grant/Funding applications	Started	February 2017
Subject recruitment	November 1, 2016	August 1, 2017
Data Analysis	March 1, 2017	August 30, 2017
Thesis/Report	November 15, 2017	December 1, 2017

Required Resources & Budget

Resource	Estimated Cost
Personnel	
Consent forms, severity scale, questionnaire, other paper documents	
Counseling office	

\$10 gift cards for return visit, 104 subjects	\$1040.00
--	-----------

References

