Appendix 1. TEAEs in Vaginal Conjugated Estrogens Cream and Ospemifene Trials				
	Ospemifene 60mg x 12 weeks [17]	Ospemifene 60mg x 52wks [7]	Vaginal CE 0.3mg x 12 weeks [30]	Vaginal CE 0.3mg x 52 weeks [30]
% w/ 1 or more TEAE	Not stated, 1892 exposed patients total, 1000 patient years of exposure	63.8%	71.4%	61.4%
Headache	2.4%		18.6%	14.4
Muscle spasm	3.2%			
Arthralgia				9.1
Vaginal discharge	3.8%			
Vaginal candidiasis or mycotic infection		4.3%		
Vaginitis				6.1%
Hot flashes	7.5%	7.2% (1.6% discontinuation rate)		
UTI	Similar to placebo	8.7% (8.2% for placebo)		
Vaginal bleeding			*1.4% of all groups	*1% of all groups
Proliferative endometrium				0.08%
Hyperplasia or cancer	0%	0%		0%
Cardiovascular events/VTE	0.3%	0%		
URI/Nasopharyngitis/Sinusitis		5% or more		
Pharyngolaryngeal pain		5% or more		
Hypercholesterolemia		5% or more		
Serious/Severe TEAEs <5%	0.13 per patient year (0.21 in placebo group)	5 participants with 7 TESAEs: breast prosthesis implantation, encephalitis herpes, non-cardiac chest pain, candida meningitis, gastritis, chronic obstructive pulmonary disease, and dehydration	5 participants from all groups, considered unrelated to study	6 participants from all groups, considered unrelated to study
TEAE: treatment-emergent adverse event; CE: conjugated estrogens; VTE: venous thromboembolism; *: study does not distinguish between placebo and the two treatment arms.

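### Safety is to be compared between arms, yet the only adverse-event capture described is participant-initiated reporting of possibly drug-related events

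*Combined protocol and SAP*

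**What the plan says.** Safety is presented as a comparison in two places. The Introduction states: "Secondary aims include comparing markers of vaginal health and safety in both treatment groups". The Overview under Approach describes a "randomized study that will compare efficacy and safety of ospemifene and vaginal estrogen".

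Capture is described under Safety Monitoring. The contact details have a stated purpose: "Participants in the study will be provided with contact information to be used in the case of an adverse event related to the medication". Women are then told to use them "to inform the team about any adverse event that may be related to the medication". On recording, the section says: "All reports of injury will be logged in one password-protected electronic file, by members of the study team". The accumulated data, adverse events included, are reviewed every two weeks. After pointing to Appendix 1 the section adds: "This data will be used to determine whether the study will be discontinued due to occurrence or frequency of any given adverse event". No numerical threshold is given.

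Appendix 1 tabulates treatment-emergent events from earlier trials of the two drugs. It is not restricted to events judged related. The serious-event entry for vaginal conjugated estrogens at 12 weeks, for example, reads "5 participants from all groups, considered unrelated to study".

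**The concern.** A between-arm safety comparison needs events to be sought in the same way from every woman in both arms. Here a woman enters the safety data only if she decides to report and regards the event as possibly due to her drug. Two problems follow.

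- **Level.** Volunteered, attribution-filtered reports will probably fall short of the events that occur. Appendix 1 rates are not filtered by attribution, so setting the trial's counts beside them favours the trial.
- **Comparability.** Women know their treatment (Overview), are counselled on the adverse events of the assigned drug (Patient Groups) and receive that drug's insert (Study Plan). What a woman considers possibly related may therefore depend on her arm. The direction and size of any such difference are unknown, so it cannot be corrected in the analysis.

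At stake are a stated secondary objective and the use of event frequencies in deciding whether the study continues. The FSFI comparison is not affected.

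**Working it through.** **1. Is there any other capture route?** The contacts in the text are:

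- Enrolment (Patient Groups): FSFI, symptom scale, counselling.
- Next-day call (Study Plan): confirms the start date.
- Week 12, by visit or phone (Study Plan): FSFI and symptom scale.
- A four-week symptom comparison is mentioned under Specific Aim 2, but the Study Plan describes no contact for it.
- Two-weekly review (Safety Monitoring): covers data already held, with no participant contact described.

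The symptom scale covers dyspareunia, dryness, pain and itching. It would not pick up headache, hot flashes, bleeding or thromboembolism. None of these contacts is described as asking about adverse events.

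**2. Denominator.** The plan's 52 per group (Sample Size Analysis) can be reproduced from 57% v 28.5%, two-sided alpha 0.05, power 0.80 and unpooled variance:

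n = (1.96 + 0.842)² × (0.57×0.43 + 0.285×0.715) / 0.285² = 7.85 × 0.4489 / 0.0812 = 43.4, so 44; then 44 / 0.85 = 51.8, so 52.

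I use 52 per arm, and 44 as the number left after the assumed 15% dropout.

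**3. Level: hot flashes on ospemifene.** Appendix 1 gives 7.5% at 12 weeks. Expected reports = n × true rate × fraction reported. The reported fractions are assumptions, since the documents give none.

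- Reference rate, all reported: 52 × 0.075 = 3.9.
- Doubled rate, all reported: 52 × 0.15 = 7.8.
- Doubled rate, half reported: 52 × 0.15 × 0.5 = 3.9.

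Take 4 or more reports as an illustrative signal, being the first whole number above 3.9; the plan sets none. With a true rate of 15%, the exact binomial chance of reaching it is 96% with all events reported, 85% with three quarters, 55% with half and 13% with a quarter. At the reference rate with full reporting it is also 55%. Under half reporting, a doubled rate cannot be told apart from the reference rate.

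**4. Comparability: equal truth, unequal reporting.** Assume that 65% of women in each arm truly have at least one event. The observed rate in an arm is p = 0.65 × fraction reported. For a two-sided pooled two-proportion test at 0.05,

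P(p<0.05) ≈ Φ{ [ |p₁−p₂|√n − 1.96√(2p̄(1−p̄)) ] / √(p₁(1−p₁)+p₂(1−p₂)) },

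plus an opposite tail of less than half a percentage point when reporting is unequal. For 60% v 40% reporting, p₁ = 0.39, p₂ = 0.26 and p̄ = 0.325. At n = 52 this is (0.937 − 1.298)/0.656 = −0.550, and Φ = 0.29.

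| Reporting fractions | Observed rates | 52 per arm | 44 per arm |
|---|---|---|---|
| equal | equal | about 5% | about 5% |
| 50% v 40% | 32.5% v 26% | 11% | 10% |
| 60% v 40% | 39% v 26% | 29% | 25% |
| 40% v 20% | 26% v 13% | 39% | 33% |

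The plan specifies no safety test. The table only shows how far a conventional comparison could mislead.

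**The case against.** The best counter-argument is that safety is a minor part of this trial. Both lists of Specific Aims cover only sexual function and atrophy symptoms, and no safety endpoint or analysis is defined. That is true, but the Introduction and the Overview still promise the comparison. Withdrawing the comparative safety claim would remove that inconsistency, though it would leave the under-counting in the monitoring data.

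The text available is also incomplete. The contact route is removed, the study-plan figure is not shown, and the intake packet's adverse-event instructions are listed but not reproduced. A reader might infer that events are accepted only by telephone. The documents do not say so; they show only that reporting is left to the participant. The finding therefore rests on the text available.

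A reader might also infer that the study-level check could never lead to discontinuation. The documents do not support that. No threshold exists, occurrence as well as frequency counts, and one serious event might suffice. The Individual Stopping Rules carry no relatedness condition, although they too depend on the team learning of the event.

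Finally, the numbers depend on assumptions. The any-event rates stated in Appendix 1 run from 61.4% to 71.4%, but only the 71.4% (vaginal conjugated estrogens) is a 12-week figure. The 63.8% and 61.4% are 52-week figures, and the 12-week ospemifene rate is not stated. The 65% is thus an assumption, as are all the reporting fractions. How the earlier trials collected events is not visible either. These limits affect the size of the effect, not the mismatch between the stated objective and the data collected for it.

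**Conclusion.** The concern stands in this form: a between-arm safety comparison is promised, and the only capture described is participant-initiated and limited to possibly related events. Followed as written, this will probably under-count, and it tends to make the trial look safer than it is beside Appendix 1. Between arms there is a risk of bias, not a demonstrated bias, and its direction and size are unknown.

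The size depends on unknown reporting. The chance of a spurious difference runs from about 5% under equal reporting to 39% at 40% v 20% with 52 per arm (33% with 44), given equal true rates of 65%. A doubling of the hot-flash rate would be hidden if half of the cases were reported. The objective and the monitoring data need repair, but the main efficacy comparison does not depend on it.

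**What to change.** 1. In Safety Monitoring, remove the relatedness condition, both from the purpose of the contact details and from the instruction to women, so that they are told to report any adverse event. This also improves the data reaching the two-weekly review, which a week-12 question alone would not do.
2. At the existing week-12 contact, by visit or phone, ask all women in both arms the same open question plus a short checklist built from the Appendix 1 rows. Record every event regardless of attribution. Attempt the same questions at withdrawal for women who stop early: with an assumed dropout of at least 15% and withdrawals under the stopping rules, week 12 will not reach everyone.
3. Tabulate the counts by randomised arm for the safety comparison, showing volunteered and solicited events separately. State that any comparison with Appendix 1 is approximate, because collection methods may differ and a checklist may raise counts.

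The cost is about one page added to the week-12 questionnaire, a few minutes per woman, and an attempted contact at withdrawal. No new scheduled visit is needed and the sample size is unchanged. The remaining weaknesses are recall over 12 weeks, higher recorded counts, expectation bias from open-label treatment, and no data from women lost to follow-up.

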In its clinical development, ospemifene was singled out because unlike tamoxifen and raloxifene, ospemifene significantly improves vaginal maturation. As a non-estrogen substance, its mechanism involves activation of estrogen receptors in the vagina, which leads to an increased thickness, mucification, and vacuolization of vaginal epithelium [18]. Several RCTs have shown an improvement in VVA with the use of ospemifene compared to placebo [6]. Importantly, the serum estradiol levels have been documented as unchanged in patients that use the medication for 12 weeks [19].

Equally important is the activity of ospemifene in mammary tissue. In ER+ human breast cancer cells, ospemifene has either had no impact, or has had a dose-dependent growth inhibitory effect [20,21]. This implies its dependence on ER-alpha expression in this tissue. Two studies examined ospemifene's ability to prevent dimethylbenzanthracene (DMBA)-induced breast cancer in mice. For up to 52 weeks of drug exposure, ospemifene prevented breast tumor formation similarly to tamoxifen [22]. Moreover, in normal human breast tissue, ospemifene also has similar antiestrogenic inhibitory effects as tamoxifen [23].

An additional pilot study involving ospemifene administration to rhesus macaques suggest that it has a lower carcinogenic potential than tamoxifen, which is another SERM that is used in breast cancer treatment and prevention. In this study, there was no evidence of DNA adduct production in the liver or the endometrium from daily ospemifene, while tamoxifen, the positive control, showed production of several DNA adducts in each organ [24]. Furthermore, clinical trials mirrored animal studies in that there was an increase in uterine weight and proliferative tissue, but there has never been any evidence of endometrial hyperplasia or bleeding with use of ospemifene [25,26]. These findings have been strengthened by six RCTs, where no cases of endometrial hyperplasia or cancer has been identified [6].

Sexual Health

As may be expected, VVA is four times more likely in patients who suffer from sexual dysfunction [14]. Ospemifene is FDA-approved specifically for dyspareunia in postmenopausal women with VVA. Studies show that it also improves the overall sexual health for women [12]. While estrogen has been shown to improve dyspareunia and lubrication, its impact on overall sexual health is not well-identified [27].

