To our knowledge, there has been no prior study that reported the prevalence of female sexual dysfunction amongst women using vaginal conjugated estrogens, defined as having an FSFI score of 26.55 or less. With an FSD prevalence of 57%, we determine a 50% reduction in the prevalence to be clinically significant. Setting an alpha of 0.05, and a power of 0.80, and assuming a minimum of 15% dropout rate, the sample size is set to 52 in each group.

Specific Aims

Specific Aim 1: To compare the efficacy of each drug in improving sexual function.

- a. Experimental Design: In this study, participants will be asked to complete the 19-question female sexual function index (FSFI) questionnaire at the beginning of the study period and at 12 weeks. The results will be used to compare the effect of each medication on the various domains of sexual function.

The mean total score in each treatment group at baseline will be compared using Student's t-test. Additionally, the score of the components of desire, arousal, lubrication, orgasm, satisfaction and pain will be similarly compared. Later, the change in these scores between the two treatment groups at 12 weeks will be compared using a paired t-test analysis.

Anticipated Results and Interpretation: We expect to see similar results in this study, showing comparable improvements in vaginal lubrication and dyspareunia, while showing greater improvement for overall sexual health in the ospemifene group.

Potential Pitfalls, Alternative Approaches, and Future Directions: We do not anticipate any challenges with the administration and analysis of this questionnaire.

Specific Aim 2: To compare each drug's impact on VVA symptoms

- a. Experimental Design: Participants will complete a Likert scale of symptom severity at the beginning and at the end of the study. The symptoms listed will include dyspareunia, vaginal dryness, vaginal pain, and vaginal itching. The survey will ask them to rate the severity of each VVA symptom on a scale of 0 to 3, with 0 being none, 1 being mild, 2 being moderate, and 3 being severe. It will also ask them to choose their most bothersome symptom (MBS).

The mean score of the MBS in each treatment group at baseline will be compared using Student's t-test. Later, the change in score of the MBS between the two treatment groups at four weeks and again at 12 weeks will be compared using a paired t-test analysis.

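### The individual stopping rule ties stopping the drug to leaving the study, so a woman with a listed event before week 12 loses her only planned post-baseline FSFI (small effect, cheap to fix)

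*Combined protocol and SAP*

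**What the plan says.** Individual Stopping Rules lists four triggers: new vaginal bleeding, a cardiovascular event, a venous thromboembolism and a new cancer diagnosis. Each "will require the individual to discontinue the medication and withdraw from the study". Both actions are compulsory.

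Specific Aim 1 (in the section after Sample Size Analysis) has participants complete the FSFI "questionnaire at the beginning of the study period and at 12 weeks". Study Plan agrees: there is one return at 12 weeks for the FSFI and the symptom scale, and the questionnaires may be done by phone. A four-week time point appears only in the analysis text of Specific Aim 2, for the most bothersome symptom.

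Under Safety Monitoring, participants are told to contact the team "to inform the team about any adverse event that may be related to the medication". Reports are logged, and "Patient data, including adverse events will be reviewed every two weeks".

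Sample Size Analysis takes a prevalence of sexual dysfunction (FSFI 26.55 or less) of 57%, states "we determine a 50% reduction in the prevalence to be clinically significant", and allows for at least 15% dropout, giving 52 women per arm. The visible text describes no early-termination FSFI, no follow-up after the drug is stopped, no analysis set and no method for missing data.

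**The concern.** The rule merges two decisions that should be separate. Taking a woman off the drug after a serious event is a safety measure. Ending data collection adds no protection, and it is imposed even on a woman who would willingly answer a questionnaire by phone.

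Week 12 is the only post-baseline FSFI, so any trigger before then removes her from the primary comparison and from the 12-week symptom comparison. A four-week symptom score might survive if the event came later, but no four-week FSFI exists.

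The missingness is produced by an event after randomisation that may be caused by treatment and may occur at different rates in the two arms. Women who remain are then compared after selection on that event. A dropout allowance replaces lost numbers; it does not address selective loss.

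**Working it through.** **Step 1: the plan's own sample size.** Inputs from Sample Size Analysis: 57% versus 28.5% (half of 57%), alpha 0.05 (two-sided assumed, since sidedness is not stated), power 0.80, 15% dropout. With unpooled variance:

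n = (1.96 + 0.8416)² × [0.57 × 0.43 + 0.285 × 0.715] / 0.285² = 7.849 × 0.4489 / 0.0812 = 43.4, so 44 per arm.

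44 / 0.85 = 51.8, so 52 per arm. The stated figure reproduces. Planned dropouts are 0.15 × 104 = 15.6 women.

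**Step 2: how many women the rule would remove.** Rates come from Appendix 1:

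- Vaginal bleeding, 12-week vaginal estrogen trial: 1.4%. The footnote says the "study does not distinguish between placebo and the two treatment arms".
- Cardiovascular events/VTE, ospemifene: 0.3% in the 12-week column, 0% in the 52-week column. No rate is given for estrogen.
- Hyperplasia or cancer: 0% where reported. Other cancers are not given, so no rate is added.

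The Ospemifene section says "there has never been any evidence of endometrial hyperplasia or bleeding with use of ospemifene", so one reading applies bleeding to the estrogen arm only:

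- Estrogen bleeding: 52 × 0.014 = 0.73.
- With no cardiovascular/VTE events: total 0.73.
- With 0.3% scaled to 12 weeks: the 12-week column gives "1892 exposed patients total, 1000 patient years of exposure", a mean of 1000/1892 years = 27.6 weeks. Then 52 × 0.003 × 12/27.6 = 0.07, total 0.80. This assumes that the 0.3% has that denominator, which the table does not say, and that events accrue evenly.
- With 0.3% taken as a 12-week rate: 52 × 0.003 = 0.16, total 0.88.

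Applying the pooled bleeding rate to both arms gives more:

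- Bleeding in both arms, cardiovascular/VTE in ospemifene only: 0.73 + 0.88 = 1.61.
- Both rates in both arms: 104 × (0.014 + 0.003) = 1.77.

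The range is therefore about 0.7 to 1.8 women, or 0.73/15.6 = 4.7% to 1.77/15.6 = 11.3% of the planned dropouts.

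**Step 3: will the rule be used at all?** Chance of at least one trigger:

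- Estrogen bleeding only: 1 − 0.986^52 = 52%.
- Adding 0.3% in the ospemifene arm: 1 − 0.986^52 × 0.997^52 = 59%.
- 1.7% in both arms: 1 − 0.983^104 = 83%, with a 26% chance of three or more.

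**Step 4: power, if these losses come on top of the 15%.** Two-sided two-proportion test with pooled variance (slightly more demanding than Step 1, hence below 0.80 at 44 per arm):

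| Analysable women | Power |
|---|---|
| 44 v 44 | 0.781 |
| 43 v 44 | 0.776 |
| 44.2 per arm (15% lost) | 0.783 |
| 43.3 per arm (15% + 1.7% lost) | 0.774 |

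The cost is about 0.5 to 0.9 percentage points. If the losses fall within the 15%, it is nil.

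**Step 5: possible distortion.** With 44 others observed in an arm and k women lost, the largest shift in the proportion with FSFI 26.55 or less is k × max(p, 1 − p)/(44 + k):

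| | p = 0.57 | p = 0.285 |
|---|---|---|
| k = 1 | 0.57/45 = 1.3 points | 0.715/45 = 1.6 points |
| k = 2 | 1.14/46 = 2.5 points | 1.43/46 = 3.1 points |

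The design difference is 28.5 points. These figures are conditional on k and concern the dichotomised FSFI used for the sample size. The planned analysis compares mean scores and changes. There, one lost woman whose change differs by d points from the average of the other 44 moves the arm mean by d/45, about 2% of d. The documents give no FSFI standard deviation, so this cannot be set against the precision of the comparison.

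**The case against.** The strongest reply is that this is too small to matter. On the lower rates there is a 41% to 48% chance that nobody is affected, and the 15% allowance is described as a minimum. The affected women are a small fraction of all expected missing FSFI scores, and the fix does nothing for the rest. That stands as a limit on size. It does not justify a rule that makes the loss compulsory.

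Second, the aim is efficacy, and a sexual-function score taken off drug after a thrombosis or a cancer diagnosis may measure the event. This is a real downside. But leaving these women out does not yield an on-drug effect either; it compares whoever remained event-free. A collected score can be handled in more than one way, whereas an uncollected one cannot be recovered.

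Third, Appendix 1 offers no between-arm comparison. The bleeding rate is pooled with placebo, and the absence of bleeding on ospemifene rests on one background sentence. This stands: imbalance between arms is possible, not shown.

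A reader might also infer that the rule loses the safety events themselves, or that events are not followed to their outcome. The documents do not support either. Events are reported, logged and reviewed every two weeks. Whether they are followed after withdrawal cannot be judged, because the consent pages, the study-plan figure and the content of the intake packet are not visible.

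**Conclusion.** The point holds as a minor one. Followed as written, the rule discards the only planned post-baseline FSFI and the 12-week symptom scores of any woman with a listed event before week 12, for a reason that is not plainly random, and nothing in the visible text retrieves them.

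The expected number is roughly 0.7 to 1.8 of 104. This rests on rates taken from different trials, a bleeding rate pooled over arms, and no cardiovascular/VTE rate for estrogen, so 1.8 is not a ceiling.

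Two stronger readings should be resisted. A reader might infer that the trial would be biased towards one drug, but nothing in the documents links these events to better or worse FSFI, so the direction is unknown. A reader might infer a loss of power, but within the dropout allowance there is essentially none.

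**What to change.** Keep the requirement to stop the drug. Replace the requirement to leave the study with a sentence to this effect: unless she withdraws consent, a woman who stops treatment under this rule remains in follow-up, completes the FSFI and symptom scale at 12 weeks, by phone if necessary, and is analysed in the arm to which she was randomised.

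The cost is one protocol sentence, a matching change in the consent form if it repeats the rule, and one or two phone calls for each woman affected. The price in interpretation is that her 12-week scores include time off drug and may reflect the event, so the report should state how many such scores there are in each arm.
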